10.3. Analysis Populations

10.3.1. Safety

All randomized subjects who receive at least 1 application of study drug will be included in the Safety population. Subjects will be analyzed as treated.

10.3.2. Intent-To-Treat

All randomized subjects will be included in the Intent-to-treat (ITT) population. Subjects will be analyzed as randomized.

10.3.3. Per-Protocol

All subjects in the ITT population who did not have any major protocol deviations will be included in the Per Protocol (PP) population. Subjects will be analyzed as treated.

10.3.4. Pharmacokinetic

All subjects who undergo plasma PK sampling and have evaluable concentration-time data for analysis will be included in the PK population. A sample that is below the limit of quantification (BLQ) of the assay is considered evaluable.

10.4. Planned Analyses

All efficacy and safety measures over the course of the study will be presented. Details of planned analyses will be described in the Statistical Analysis Plan (SAP), which will be finalized prior to database lock.

10.4.1. Disposition and Demographics

Demographic and baseline characteristics as well as medical history will be summarized using the ITT population, including frequency and percentages for categorical variables and mean, standard deviation, median, minimum, and maximum for continuous variables.

The numbers of subjects in the different analysis populations will be summarized by treatment group, including overall categories.

10.4.2. Efficacy Analyses

All efficacy analyses will be based on the ITT population and will be repeated for the PP population only for the primary and secondary efficacy endpoints as supportive analysis.

10.4.2.1. Primary Endpoint Analyses

The primary efficacy endpoint is proportion of subjects who achieve PGA score of clear (0) or almost clear (1) with a minimum 2-grade improvement from Baseline at Week 12. The primary efficacy endpoint will be analyzed using a Cochran–Mantel–Haenszel (CMH) test stratified by PGA score at Baseline (PGA scores of 2, 3 or 4).

10.4.2.2. Secondary and Exploratory Efficacy Endpoint Analyses

The secondary efficacy endpoints are as follows:

- Proportion of subjects with $\geq 75\%$ improvement in PASI from Baseline at Week 12
- Mean change in %BSA affected from Baseline to Week 12
- Proportion of subjects with a PGA score of 0 or 1 at Week 12
- Proportion of subjects with $\geq 90\%$ improvement in PASI score from Baseline to Week 12

Exploratory efficacy endpoints are as follows:

- Time to achieve a PGA score of 0 or 1 with a minimum 2-grade improvement from Baseline
- Proportion of subjects with a PGA score of 0 or 1 at Weeks 2, 4, and 8
- Proportion of subjects who achieve a PGA score of 0 or 1 with a minimum 2-grade improvement from Baseline at Weeks 2, 4, and 8
- Mean absolute and percent change in PASI score from Baseline to Weeks 2, 4, 8, and 12
- Proportion of subjects with $\geq 50\%$ improvement in PASI score from Baseline to Weeks 2, 4, 8, and 12
- Proportion of subjects with $\geq 75\%$ improvement in PASI score from Baseline to Weeks 2, 4, and 8

- Proportion of subjects with $\geq 90\%$ improvement in PASI score from Baseline to Weeks 2, 4, and 8
- Mean change in %BSA affected from Baseline to Weeks 2, 4, and 8

The same methods as discussed for the primary analyses will be used to analyze all dichotomized secondary endpoints. The secondary efficacy endpoints will be tested sequentially in the order listed. Testing will stop if non-significance (2-sided $p \geq 0.05$) is observed.

Other efficacy endpoints will be analyzed using CMH test for proportions, and analysis of covariance (ANCOVA) model for continuous variables. CMH tests will be stratified by baseline PGA score, and ANCOVA models will include PGA score as a covariate.

All endpoints will be summarized descriptively as follows: continuous data will include the mean, SD, minimum, maximum, median, and number of observations; descriptive summary statistics for categorical data will include frequency counts and percentages.

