5.2. Randomization/Treatment Assignment

For the double-blind, vehicle-controlled phase of the study, subjects will be randomized at a ratio of 2:1 to receive tapinarof cream, 1% or vehicle cream as follows:

Randomization in Double-Blind, Vehicle-Controlled Phase	
Regimen	Number of Subjects
Tapinarof cream, 1% once daily for 12 weeks	Approximately 333 Subjects
Vehicle cream once daily for 12 weeks	Approximately 167 Subjects

Randomization will be stratified by baseline PGA score so that subjects with mild and severe psoriasis (PGA scores of 2 and 4, respectively) will be limited to approximately 10% each of the total randomized population, and the majority of the enrolled subjects (approximately 80%) will have a PGA score of 3, signifying moderate disease.

The randomization lists will be generated using a validated system, which involves a pseudo-random number generator so that the resulting treatment will be both reproducible and non-predictable. Access to the codes will be controlled and documented.

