10.2. Determination of Sample Size

It is assumed that the proportion of subjects who achieve PGA score of clear (0) or almost clear (1) with a minimum 2-grade improvement from Baseline at Week 12 will be 40% for subjects receiving tapinarof compared with 15% for subjects receiving vehicle control. With 500 subjects randomized in a 2:1 ratio (approximately 333 subjects receiving tapinarof cream, 1% and approximately 167 subjects receiving vehicle cream) there will be > 99% power for a statistical significance (2-sided $p < 0.05$). If tapinarof response rate is 35%, and vehicle response rate is 20%, the power will be > 94%. The power is calculated from a Fisher Exact sample size calculation which is conservative. It is assumed that up to 25% of the subjects will be lost to follow-up by 12 weeks. These subjects will be included in the primary analysis using the multiple imputation method.

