10.4.4. Analysis of Functional Outcomes and Quality of Life Endpoints

The subject-reported endpoints to examine the effect of study drug on psoriasis symptom severity and the associated impact on daily activities and attitudes are as follows:

- Change in Peak Pruritus-NRS from Baseline at Weeks 2, 4, 8, and 12
- Change over time in psoriasis impact on daily activities, as measured by the DLQI total and individual dimension scores
- Change over time in psoriasis symptoms, as measured by the PSD
- Change over time in physical component score and mental component score, as measured by the SF-36 questionnaire

Change from baseline in DLQI , PSD, SF-36, and Peak Pruritus-NRS scores will be analyzed using an ANCOVA model with treatment as a main effect, and baseline as a covariate.

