## **11. DATA CONVENTIONS FOR ANALYSIS**

### **11.1 General Statistical Principles**

All statistical tests will be performed at the 0.05 (two-sided) level of significance.

All observed and derived variables (e.g., change from baseline, percentage change from baseline, and response status) that are analyzed or summarized will be listed by subject. Descriptive statistics will provide an overview of the efficacy and safety results. For categorical parameters, the number and percentage of subjects in each category will be presented. The denominator for percentage will be appropriate for the purpose of the analysis. For continuous parameters, descriptive statistics will include number of subjects, mean, standard deviation (SD), median, minimum, and maximum.

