### **12.8.2 Secondary and Exploratory Efficacy Analyses**

The same methods as discussed for the primary analyses will be used to analyze all dichotomized and continuous secondary endpoints. The secondary efficacy endpoints will be tested sequentially in the order listed. Testing will stop if non-significance (2-sided  $p \geq 0.05$ ) is observed as described in Section 11.6.

Other exploratory efficacy endpoints will be analyzed using CMH test for proportions, and analysis of covariance (ANCOVA) model for continuous variables. CMH tests will be stratified by baseline PGA score, and ANCOVA models will include baseline PGA score as a covariate (2, 3 or 4), and baseline value of the endpoint as a continuous covariate. For proportions, the same MI approach describe above will be taken to deal with missing data. For continuous variables, the standard MI procedures for ANCOVA will be followed. Least squared means of treatment difference (tapinarof – placebo) along with the 95% CI will be reported.

Time to achieving a PGA success will be analyzed with the Kaplan Meier method in the ITT population based on Observed Cases. Treatment groups will be compared using a log-rank test. Estimates of median time to response from Kaplan Meier distribution will be computed. A Kaplan-Meier figure will also be generated.

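### Continuous endpoints go to an unqualified ANCOVA under 2:1 allocation; if the arms differ in spread, the default single residual variance misstates the standard error, and the SAP does not name a workable method for %BSA change

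*Protocol*

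**What the plan says.** **Allocation.** Protocol 5.2: "subjects will be randomized at a ratio of 2:1 to receive tapinarof cream, 1% or vehicle cream". Protocol 10.2 puts this at "approximately 333 subjects receiving tapinarof cream, 1% and approximately 167 subjects receiving vehicle cream".

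**Model.** Protocol 10.4.2.2 reserves the primary (CMH) method for the dichotomized secondary endpoints. Other efficacy endpoints that are continuous get an "analysis of covariance (ANCOVA) model for continuous variables" with PGA score as covariate, so %BSA change falls to ANCOVA there. Under Protocol 10.4.4, the patient-reported scores are "analyzed using an ANCOVA model with treatment as a main effect, and baseline as a covariate".

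**SAP detail.** SAP 12.8.2 adds the baseline value as a covariate and promises least-squares mean differences with 95% intervals. On missing data it says: "For continuous variables, the standard MI procedures for ANCOVA will be followed". It names ANCOVA, however, only for the other exploratory endpoints. It sends both the dichotomized and the continuous secondary endpoints to the primary method, which SAP 12.8.1 defines as a CMH analysis combined on the log relative risk. SAP 12.8.3 uses ANCOVA for DLQI, PSD, SF-36 and Peak Pruritus-NRS, and gives the daily itch difference an interval without naming a model.

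**Missing data.** SAP 9 and the table in SAP 12.8 impute %BSA and PASI and analyse the patient-reported endpoints as observed cases.

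**Level.** SAP 11.1: "All statistical tests will be performed at the 0.05 (two-sided) level of significance".

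Neither document mentions a robust or arm-specific variance, or a sensitivity analysis for unequal spread.

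**The concern.** Ordinary ANCOVA estimates one residual variance and applies it to both arms. Under equal allocation, a difference in spread cancels out of the standard error of the treatment difference. Under 2:1 it does not: the pooled variance is weighted towards the larger tapinarof arm, while the smaller vehicle arm has the larger weight in the true variance of the difference.

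Unequal spread is plausible if the drug works, and in either direction. %BSA cannot fall below zero, so treated scores may bunch near clear while vehicle scores stay spread out. Alternatively, a mixture of responders and non-responders may widen the tapinarof arm.

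What is at stake is the calibration of the intervals promised in SAP 12.8.2 and of the ANCOVA p-values. One of those endpoints matters for confirmatory claims. %BSA change is in the fixed sequence of SAP 11.6 and comes before PASI-90 both there and in Protocol 10.4.2.2, so its p-value decides whether PASI-90 is tested.

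**Working it through.** **1. The plan's own figures.** The only power statements concern the binary primary endpoint. Protocol 10.2 assumes the response rate "will be 40% for subjects receiving tapinarof compared with 15% for subjects receiving vehicle control", and 35% versus 20% as a second case. Full enumeration of the two-sided Fisher test at 333 versus 167 gives 99.998% (stated: above 99%) and 93.8% (stated: above 94%; the pooled normal approximation gives 94.5%). These agree within rounding. No standard deviation, power or interval width is given for any continuous endpoint, so there is no stated figure to reproduce on this point.

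**2. Closed form.** Let k be the residual variance in the vehicle arm divided by that in the tapinarof arm (assumed), with tapinarof set to 1.

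- Variance the model uses: P = [(333 + 167k)/500] × (1/333 + 1/167)
- True variance: T = 1/333 + k/167
- SE ratio: q = √(P/T)
- Coverage of a nominal 95% interval: 2Φ(1.96q) − 1

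For k = 2: P = (667/500) × 0.008991 = 0.011994; T = 0.003003 + 0.011976 = 0.014979; q = √0.8007 = 0.895.

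| k | P | T | q | Coverage |
|---|---|---|---|---|
| 2 | 0.01199 | 0.01498 | 0.895 | about 92% |
| 1.5 | 0.01049 | 0.01199 | 0.936 | about 93% |
| 1 | 0.00899 | 0.00899 | 1.000 | 95% |
| 0.67 | 0.00800 | 0.00702 | 1.068 | about 96% |
| 0.5 | 0.00749 | 0.00600 | 1.118 | about 97% |

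At 1:1 allocation q is 1.000 for every k, so the problem needs unequal allocation and unequal spread together. Equal dropout in both arms leaves q unchanged.

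**3. Complete-data simulation.** ANCOVA on treatment, baseline PGA (10/80/10%) and baseline %BSA (uniform, 3 to 20), 6,000 runs per case. At vehicle/tapinarof SD ratios of 0.5, 0.8, 1, 1.25, 1.5 and 2 (variance ratios 0.25 to 4), the ordinary SE covered 98.1%, 97.0%, 94.5%, 93.2%, 91.1% and 89.1%. The HC3 SE covered 94.2% to 95.4% throughout.

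**4. With imputation.** Two simulations assumed 25% of values missing at random, the ceiling in Protocol 10.2, and imputed by ordinary regression with one residual variance. With 20 imputations, coverage with the ordinary SE and then HC3 was 91.6% and 93.6% at k = 2, 93.3% and 94.5% at k = 1.5, and 97.2% and 96.5% at k = 0.5. With 15 imputations it was 92.6% and 93.9% at k = 2, and 97.4% and 96.4% at k = 0.5. HC3 removes part of the error. The remainder is consistent with the imputation model itself pooling the variance.

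**5. What the plan's response rates suggest.** If spread came only from a responder/non-responder split, variance would be proportional to p(1 − p). That gives 0.15 × 0.85 = 0.1275 against 0.40 × 0.60 = 0.24, so k = 0.53, or 0.16 against 0.2275, so k = 0.70. Coverage would be about 97% and 96%, that is, intervals too wide. Other sources of variance would dilute this, and the floor on %BSA can push the other way.

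**The case against.** The strongest reply has four parts.

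- **The pooled variance is not written down.** True. It is inferred from the ANCOVA default. But an analyst following the text as it stands would fit that default.
- **Direction and size are unknown, and the effect may be small.** This also stands. SD ratios between 0.8 and 1.25 keep coverage between about 93% and 96.5%, and ratios below 1 make the planned intervals conservative.
- **No decision is shown to change.** This stands in part. The primary endpoint and three of the four secondaries are binary, and most continuous endpoints are exploratory. No scenario has been worked in which the %BSA test flips. If treatment has no effect at all, both arms share one distribution and the test remains valid. Even so, %BSA change does control access to PASI-90.
- **A robust SE alone does not repair the imputed analyses.** Correct, as step 4 shows; the fix has to allow for it.

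A reader might infer that every continuous endpoint, %BSA change included, is explicitly committed to a pooled-variance interval that will be too narrow. The documents do not support that. SAP 12.8.2 literally puts %BSA change under the CMH method, the daily itch interval has no named model, and the ANCOVA paragraph for the patient-reported scores in SAP 12.8.3 promises no interval. Nor is the combination step a problem for those scores, because they are not imputed.

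**Conclusion.** The point holds in limited form. Given 2:1 allocation and the default single residual variance, the ANCOVA standard errors are wrong to the extent that the arms differ in spread, and the plan has no safeguard. For assumed variance ratios from 0.5 to 2, nominal 95% coverage runs from about 97% down to about 92%. Since no standard deviations are given, it cannot be said which side of 95% the trial will fall on. That is a reason to prespecify a variance that is valid either way; it is not evidence of anti-conservative results. The primary and binary secondary analyses are not directly affected.

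A related gap needs no assumption. SAP 12.8.2 gives no workable method for %BSA change, because a relative-risk analysis cannot estimate a mean change.

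This is worth correcting before database lock, but it does not threaten the primary conclusion.

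**What to change.** 1. In SAP 12.8.2, name ANCOVA explicitly as the method for %BSA change, in line with Protocol 10.4.2.2.
2. In SAP 12.8.2 and 12.8.3 (and Protocol 10.4.2.2 and 10.4.4 if amended), keep the ANCOVA point estimate. Take its standard error, interval and p-value from an HC3 variance, or from a model with a separate residual variance per arm (for example PROC MIXED with REPEATED / GROUP=TRTPN).
3. For the imputed endpoints (%BSA, PASI), do this within each imputed dataset and pass that standard error to PROC MIANALYZE. Consider imputing separately by arm, because the planned FCS regression also pools the variance.
4. For the observed-case endpoints (Peak Pruritus-NRS, DLQI, PSD, SF-36), apply the robust standard error directly, with no MIANALYZE step.

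The cost is a few SAP sentences and slightly more programming, using data already collected. When the arm variances are equal, results are essentially unchanged.

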10.4.3. Safety Analyses

The Safety Population will be used in the analysis of safety data. Data will be listed by subject and treatment and summarized by treatment. No formal statistical comparisons will be made for safety data.

The number and proportion of subjects with TEAEs will be summarized by treatment, system organ class, and preferred term for all TEAEs, all TEAEs considered by the Investigator to be related to study drug, all SAEs, and all TEAEs leading to study drug discontinuation. Summaries of AEs will be presented separately for double-blind and open-label treatment phases. All AE summaries will include information for AEs that occurred after administration of the first dose of study drug until completion of the final study visit. Data listings will be provided for subjects who discontinued the study due to an AE and for subjects with an SAE.

Selected laboratory data will be analyzed using descriptive summary statistics and will be presented by study visit and treatment group, including the number of non-missing observations, mean and SD, median, upper and lower quartiles, minimum and maximum for values and changes from Baseline. Categorical safety data will be analyzed using frequency tables and, if applicable, shift tables.

Vital signs will be listed by subject and summarized by visit.

Mean scores from the LTS will be summarized by visit.

10.4.4. Analysis of Functional Outcomes and Quality of Life Endpoints

The subject-reported endpoints to examine the effect of study drug on psoriasis symptom severity and the associated impact on daily activities and attitudes are as follows:

- Change in Peak Pruritus-NRS from Baseline at Weeks 2, 4, 8, and 12
- Change over time in psoriasis impact on daily activities, as measured by the DLQI total and individual dimension scores
- Change over time in psoriasis symptoms, as measured by the PSD
- Change over time in physical component score and mental component score, as measured by the SF-36 questionnaire

Change from baseline in DLQI , PSD, SF-36, and Peak Pruritus-NRS scores will be analyzed using an ANCOVA model with treatment as a main effect, and baseline as a covariate.

10.4.5. Pharmacokinetic Analyses

Data will be listed and summarized. Listings will be sorted by subject, day, and time; summaries will be presented by study visit and time from last dose.

Unless stated otherwise, descriptive summaries for continuous variables will include n, mean, SD, median, minimum, and maximum. If data permit, time to steady state will be assessed using the sampled trough values. Exploratory analyses may include relationships of plasma concentrations with patient demographics or AEs.

10.5. Interim Analyses

No interim analyses will be performed from a statistical standpoint.

10.6. Handling of Missing Data

Every effort will be made to collect complete data at all visits.

The primary method of handling of missing data will utilize Multiple Imputations (MI). For sensitivity analysis, Treatment Failure (TF) will be imputed for missing data.

For the MI model, 100 imputations will be generated using PROC MI of SAS. Fully Conditional Specification (FCS) model using the regression method will be used with the response (eg, PGA score) at prior post-baseline visits, baseline strata, and treatment group as covariates, The ROUND and MINIMUM options will be utilized to ensure imputed values are non-negative integers. The seed to be used is 20180330. The results of the 100 analyses will be transformed into a normal statistic and combined into a single analysis using PROC MIANALYZE.

11. RESPONSIBILITIES

11.1. Investigator Responsibilities

11.1.1. Good Clinical Practice

The Investigator will ensure that this study is conducted in accordance with the principles of the “Declaration of Helsinki” (as amended in Edinburgh, Tokyo, Venice, Hong Kong, and South Africa), International Conference on Harmonization (ICH) guidelines, or with the laws and regulations of the country in which the research is conducted, whichever affords the greater protection to the study subject. For studies conducted under a United States Investigational New Drug Application (IND), the Investigator will ensure that the basic principles of “Good Clinical Practice,” as outlined in 21 Code of Federal Regulations (CFR) 312, subpart D, “Responsibilities of Sponsors and Investigators,” 21 CFR, part 50, 1998, and 21 CFR, part 56, 1998, are adhered to. These standards are consistent with the requirements of the European Community Directive 2001/20/EC.

Since this is a “covered” clinical trial, the Investigator will ensure that 21 CFR, Part 54, 1998, is adhered to; a “covered” clinical trial is any “study of a drug or device in humans submitted in a marketing application or reclassification petition subject to this part that the applicant or Food and Drug Administration (FDA) relies on to establish that the product is effective (including studies that show equivalence to an effective product) or that make a significant contribution to the demonstration of safety.” This requires that Investigators and all sub-investigators must provide documentation of their financial interest or arrangements with the Sponsor, or proprietary interests in the drug being studied. This documentation must be provided before participation of the Investigator and any sub-investigator. The Investigator and sub-investigator agree to notify the Sponsor of any change reportable interests during the study and for 1 year following completion of the study. Study completion is defined as the date that the last subject has completed the protocol-defined activities.

11.1.2. Institutional Review Board/Independent Ethics Committee Approval

This protocol and any accompanying material to be provided to the subject (such as advertisements, subject information sheets, or descriptions of the study used to obtain informed consent) will be submitted by the Investigator to an IRB or IEC. Approval from the IRB or IEC must be obtained before starting the study and should be documented in a letter to the Investigator specifying the protocol number, protocol version, protocol date, documents reviewed, and date on which the committee met and granted the approval.

Any modifications made to the protocol after receipt of IRB or IEC approval must also be submitted to the IRB or IEC for approval before implementation.

